# 4.10 Efficacy evaluation

The analysis of all efficacy endpoints, unless otherwise specified will be performed on the FAS.

# 4.10.1 Primary/Secondary Endpoint

The primary efficacy endpoint for this study is the percent change from baseline in UACR at the end of 12 weeks of study treatment (Visit 10).

Central laboratory urine samples for the determination of albumin and creatinine and calculation of UACR will be collected at the timepoints described in the SoA (Appendix A: Schedule of Activities).

Participants will collect 1st morning void urine samples at home on 3 consecutive days (ideally day of visit and preceding 2 days [refrigerated overnight] which will be returned on the day of visit).

The UACR from each urine sample will be calculated as follows:

$$UACR (mg/mmol) = 10 \times \frac{Urine \ Albumin (mg/dL)}{Urine \ Creatinine (mmol/L)}$$

At each visit, the geometric mean of the triplicate UACR values will be computed and used for the analysis of UACR. In case of missing values for UACR the geometric mean will be calculated considering the number of the available measurements. Baseline for UACR will be defined as the geometric mean of 3 consecutive days prior to the first dose of study treatment (ideally day of visit and preceding 2 days). Only samples collected prior to the first dose of study medication will be used.

As UACR is assumed to follow a log-normal distribution, it will be log transformed for statistical analysis purposes obtaining the ratio of geometric means.

Percent change from baseline in UACR at  $Visit_k$ , k in  $\{7, 8, 9, 10\}$  will be calculated as:

$$100 \times \left(\frac{GeoMean(UACR_{Visit_k})}{GeoMean(UACR_{Baseline})} - 1\right)$$

#### 4.10.1.1 Analysis of the primary efficacy endpoint

Patients randomised according to CSP versions 1.0 to 5.0 (before dropping placebo and AZD9977 150 mg monotherapy arms) will be considered as part of Cohort 1, while patients randomised subsequently will be included in Cohort 2. The primary analysis for the four treatment groups maintained in Cohort 2 will combine data from both cohorts, while the accrued data from discontinued treatment groups will be analysed descriptively.

TP-GDO-WW-016-08 CONFIDENTIAL Project Document Version No. 3.0 Effective Date: 26 Nov 19 Project Document Effective Date: Date of last signature Related to: SOP-GDO-WW-019 Page 22 of 50

The change from baseline of the log transformed UACR at the end of 12 weeks of study treatment (Visit 10) will be analysed by a mixed-effects model for repeated measures (MMRM) at Visits 7, 8, 9, and 10. The analysis model will include treatment and visit as fixed effect, the log transformed baseline UACR and the stratifying factors (T2DM [yes/no] and eGFR [ $\geq$  20 to <30 mL/min/1.73 m²; or  $\geq$ 30 to <45 mL/min/1.73 m²; or  $\geq$ 45 mL/min/1.73 m²] as well as the Cohort variable (1 or 2) as covariates. Moreover, treatment  $\times$  visit interaction will also be included in the model.

- 1. The model will involve the following four steps:
  - a) Log-transformation of the UACR:

First, the UACR at baseline and the UACR at post-baseline visits (7, 8, 9, and 10) will be log-transformed. The log-transformed UACR at baseline will then be subtracted from the log-transformed at post-baseline visits to calculate the change of UACR in log units.

b) Execution of the model:

The model will include the change in UACR in log units as a dependent variable and the log-transformed UACR at baseline as covariate, as well as the other independent variables described at the beginning of this section.

- c) Back-transformation of the results from the model:
  - The results from the execution of the model will be back transformed to the original scale after an exponentiation of the means to obtain the percent change from baseline of the treatments. The LS mean difference and its CI between each treatment and dapagliflozin alone will also be back-transformed to yield the percent difference between two treatments with its 95% CI at Visit 10 expressed in percentage.
- d) The statistics for the percent change from baseline, percent difference between treatments and percentage 95% CI (%) will be calculated as follows:
  - percent change from baseline = (exp(estimate)-1)\*100 where estimate is the LS mean
  - percent difference between treatments= (exp(estimate)-1)\*100 where estimate is the LS mean difference
  - 95% CI lower and upper (%): (exp(lower)-1)\*100; (exp(upper)-1)\*100.

An unstructured covariance structure will be used for the within-participant errors. The denominator degrees of freedom will be calculated according to the Kenward-Roger method. If the estimating algorithms do not converge, the following steps will be taken to simplify the model until convergence is achieved:

Try in order these four covariance structures: Toeplitz, the first-order autoregressive, compound symmetry and independent structure. Stop as soon as convergence is achieved.

The following comparison will be performed by the execution of a MMRM:

- 1. Overall comparison of the percentage changes from baseline in UACR at week 12 across all 4 treatment groups
- 2. Each of the 3 doses of AZD9977 in combination with dapagliflozin 10 mg versus dapagliflozin 10 mg in the following order:
  - 1. AZD9977 150 mg + dapagliflozin 10 mg versus dapagliflozin 10 mg
  - 2. AZD9977 50 mg + dapagliflozin 10 mg versus dapagliflozin 10 mg
  - 3. AZD9977 15 mg + dapagliflozin 10 mg versus dapagliflozin 10 mg

The following graph will be provided:

- Mean percentage change from baseline for UACR by visit, separately for each treatment group

All available UACR values from all visits will be used regardless of any intercurrent events. Missing values will not be imputed. In this analysis it is thus assumed that any missing UACR values are missing at random (MAR).

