9.2 Sample Size Determination

A total of 119 evaluable participants per arm will provide 80% power to detect a 30% difference in a AZD9977 dose group combined with dapagliflozin 10 mg compared to dapagliflozin 10 mg alone in percent change from baseline in UACR at 12 weeks, assuming a SD of 1.0 on the natural log-scale and alpha = 0.05. To account for approximately 5% drop-out from the study, approximately 500 participants will be randomly assigned to study intervention (125 participants per group) such that approximately 476 evaluable participants (119 per group) complete the study.

Patients randomised according to CSP versions 1.0 to 5.0 (before dropping placebo and AZD9977 150 mg monotherapy arms) will be considered as part of Cohort 1, while patients randomised subsequently will be included in Cohort 2. The primary analysis for the remaining 4 treatment groups will combine data from both cohorts, while the accrued data from discontinued treatment groups will be analysed descriptively.

9.3 **Populations for Analyses**

The following populations are defined:

Population/Analysis set	Description	
Enrolled	All participants who sign the main ICF.	
Full Analysis Set (FAS)	All participants who are randomised and either receive or do not receive any study intervention. Participants are evaluated according to the treatment assigned at randomisation. The FAS will be used for all analyses of demographic baseline characteristics and efficacy data.	
Per Protocol Set (PPS)	A subset of the FAS consisting of all participants who do not violate the terms of the protocol in a way that may affect the primary efficacy endpoint significantly. All decisions to exclude participants from the per protocol analysis set will be made and documented prior to the unblinding of the study.	
Safety Set (SS)	 All participants who are randomised and receive any study intervention. Participants are evaluated according to the actual treatment they received. If a participant received a different treatment dose than randomised throughout the study, they will be analysed according to the treated dose, not the randomisation dose. If a participant received study drug from the wrong kit for only part of the treatment duration, they will be analysed according to their randomisation dose. The SS will be used for all safety analyses. 	

Table 7Populations for Analysis

Additional analysis sets, such as PK population may be defined the SAP for exploratory analyses.

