9.4.2.1 Primary Endpoint

The primary efficacy endpoint for this study is the percent change from baseline in UACR at 12 weeks.

Baseline for UACR will be defined as the geometric mean of 3 UACR values derived from samples collected at consecutive days prior to the first dose of study treatment.

As UACR is assumed to follow a log-normal distribution, it will be log transformed for statistical analysis purposes. The mean log percent changes in UACR at 12 weeks for each of the 3 doses of AZD9977 combined with dapagliflozin 10 mg and dapagliflozin 10 mg alone will be estimated in a mixed model for repeated measures (Visits 7, 8, 9, and 10). The values will be back-transformed onto the original scale to give the geometric mean relative percent change from baseline at 12 weeks.

Patients randomised according to CSP versions 1.0 to 5.0 (before dropping placebo and AZD9977 150 mg monotherapy arms) will be considered as part of Cohort 1, while patients randomised subsequently will be included in Cohort 2. The primary analysis for the remaining 4 treatment groups will combine data from both cohorts, while the accrued data from discontinued treatment groups will be analysed descriptively.

The analysis model will include UACR baseline value, treatment, and visit as fixed effect, and the stratifying factors (T2DM [yes/no] and eGFR [≥ 20 to < 30 mL/min/1.73 m²; or ≥ 30 to < 45 mL/min/1.73 m²; or ≥ 45 mL/min/1.73 m²]) as well as the Cohort variable (1 or 2) as covariates. Moreover, treatment-by-visit interaction will also be included in the model. The final analytical approach will be described in detail in the SAP. For the primary analysis, the main treatment comparisons to be evaluated are (in a fixed-sequence testing):

- 1 Overall comparison of the percentage changes from baseline in UACR at week 12 across all 4 treatment groups
- 2 Each of the 3 doses of AZD9977 in combination with dapagliflozin 10 mg versus dapagliflozin 10 mg in the following order:
 - 1. AZD9977 150 mg + dapagliflozin 10 mg versus dapagliflozin 10 mg
 - 2. AZD9977 50 mg + dapagliflozin 10 mg versus dapagliflozin 10 mg
 - 3. AZD9977 15 mg + dapagliflozin 10 mg versus dapagliflozin 10 mg

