### 4.10.1.5 Multiple Comparisons/Multiplicity

The type I error will be controlled at a 2-sided  $\alpha$ =0.05 level for multiplicity. Statistical significance will be assessed in the pre-specified order of the endpoints as specified below. The testing procedure will continue down the hierarchy if the preceding null hypothesis is rejected at a 2-sided  $\alpha$ =0.05 level and will stop if the null hypothesis for the preceding endpoint is not rejected at a two-sided  $\alpha$ =0.05 level.

- 1. Overall comparison of the percentage changes from baseline in UACR at week 12 across all 4 treatment groups (global null hypothesis)
- 2. Each of the 3 doses of AZD9977 in combination with dapagliflozin 10 mg versus dapagliflozin 10 mg in the following order:
  - a. AZD9977 150 mg + dapagliflozin 10 mg versus dapagliflozin 10 mg
  - b. AZD9977 50 mg + dapagliflozin 10 mg versus dapagliflozin 10 mg
  - c. AZD9977 15 mg + dapagliflozin 10 mg versus dapagliflozin 10 mg

TP-GDO-WW-016-08 CONFIDENTIAL Project Document Version No. 3.0 Effective Date: 26 Nov 19 Project Document Effective Date: Date of last signature Related to: SOP-GDO-WW-019 Page 24 of 50

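### If the primary MMRM falls back from unstructured covariance, every listed alternative assumes one variance for all visits, so the Visit 10 test misses its 5% level whenever the variance differs by visit

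*SAP*

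**What the plan says.** SAP 4.10.1.1 states that change from baseline in log UACR "will be analysed by a mixed-effects model for repeated measures (MMRM) at Visits 7, 8, 9, and 10". Protocol 9.4.2.1 adds: "Moreover, treatment-by-visit interaction will also be included in the model"; the SAP has the same term. The primary comparison is at Visit 10.

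On covariance the SAP says: "An unstructured covariance structure will be used for the within-participant errors". On inference: "The denominator degrees of freedom will be calculated according to the Kenward-Roger method". The fallback has one trigger: "If the estimating algorithms do not converge, the following steps will be taken to simplify the model until convergence is achieved". The rule is then "Try in order these four covariance structures: Toeplitz, the first-order autoregressive, compound symmetry and independent structure", stopping at the first structure that converges. The section names no heterogeneous version of these structures, no empirical variance estimator, and no earlier step such as new starting values or another optimiser.

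SAP 4.10.1.5 makes the error-rate commitment: "The type I error will be controlled at a 2-sided" level of 0.05. It runs through a fixed sequence that opens with an overall four-arm test.

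The only variability figure is in Protocol 9.2, "assuming a SD of 1.0 on the natural log-scale and alpha = 0.05", repeated in SAP 4.13. It refers to 12 weeks. No SD is given for Visits 7, 8 or 9.

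**The concern.** The planned unstructured model estimates a separate variance for each visit, so its Visit 10 standard error reflects Visit 10 data. The four fallbacks, as usually defined, share one variance across Days 22, 43, 64 and 85. If log change is more variable at Day 85 than on average, the Visit 10 standard error is too small and the confidence interval too narrow. If it is less variable, the test is conservative. Kenward-Roger does not repair this, because it works within the assumed covariance.

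A rise is plausible. UACR baseline comes from the pre-randomisation visit, and correlation with it may weaken over 12 weeks, which would raise the baseline-adjusted variance. The documents neither state nor contradict this.

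At stake is the 0.05 control in SAP 4.10.1.5, in the fallback branch only. The same rule carries over to the per-protocol repeat (SAP 4.10.1.2) and, as a similar analysis, to NT-proBNP (SAP 4.10.2.2). A fallback rule cannot credibly be rewritten once results are known.

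The independent structure has a second, separate fault. It stops Visit 10 estimates from borrowing on a participant's earlier visits, which weakens the missing-at-random handling stated in SAP 4.10.1.1.

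**Working it through.** **Inputs.** From the documents: two-sided alpha 0.05; SD 1.0 on the log scale at 12 weeks; 119 evaluable and 125 randomised per arm; about 5% drop-out; four modelled visits. Assumed: the SDs at Visits 7 to 9, taken as rising or falling in roughly equal steps.

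**The plan's own figure.** A 30% difference is |ln 0.7| = 0.357. With 119 per arm and SD 1.0, SE = sqrt(2/119) = 0.1296. Power = Phi(0.357/0.1296 − 1.96) = Phi(0.791) = 78.6%, within two points of the stated 80%. This confirms how SD and alpha are meant to be read.

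**Parameter counts, four visits.** Unstructured: 4 variances + 6 covariances = 10. Toeplitz: 1 + 3 = 4. AR(1) and compound symmetry: 2 each. Independent: 1. Each fallback has a single variance.

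**Formula.** With treatment-by-visit means and near-complete data, the Visit 10 contrast is essentially the difference in Visit 10 means. Its true variance scales with the Visit 10 variance and its reported variance with the fitted common variance. Let R = Visit 10 variance / fitted common variance. Then:

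- pairwise size = 2 × [1 − Phi(1.96/sqrt(R))]
- overall four-arm size = P(chi-square on 3 df > 7.815/R)

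Under independence or compound symmetry the fitted variance is the mean of the four visit variances.

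**Worked case**, SDs 0.80, 0.87, 0.93, 1.00. Mean variance = (0.640 + 0.757 + 0.865 + 1.000)/4 = 0.815. R = 1/0.815 = 1.23. Then 1.96/sqrt(1.23) = 1.77, giving 7.7%.

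| SD, Visit 7 to Visit 10 | R | Pairwise size | Overall test |
|---|---|---|---|
| 1.0 to 1.0 | 1.00 | 5.0% | 5.0% |
| 0.9 to 1.0 | 1.11 | 6.2% | 7.0% |
| 0.8 to 1.0 | 1.23 | 7.7% | 9.5% |
| 0.7 to 1.0 | 1.36 | 9.3% | 12.5% |
| 0.6 to 1.0 | 1.51 | 11.1% | 15.9% |
| 1.0 to 0.8 (falling) | 0.78 | 2.7% | 1.9% |

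Only the ratio of SDs matters. An even rise from 0.85 to 1.15 has mean variance 1.0125 and R = 1.3225/1.0125 = 1.31, giving 8.6%. Reversed, R = 0.7225/1.0125 = 0.71, giving 2.0%.

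**Does the choice among the four matter?** Fitting each to the 0.7 to 1.0 pattern, with within-participant correlation of either compound-symmetry 0.6 or AR(1) 0.8, gives pairwise sizes of 9.2 to 9.3% for all four. The common variance drives the error, not independence.

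**Simulation.** The SAP mean model was fitted under independence with 125 per arm, 5% monotone drop-out, compound-symmetry correlation 0.6 and 4,000 runs per pattern (Monte Carlo SE about 0.35 points). For the six table patterns in order, model-based errors gave 5.0, 6.8, 8.7, 8.8, 10.9 and 2.9%. Sandwich errors gave 5.2 to 6.1%, and visit-specific variances 4.9 to 5.9%. The upper ends come from the 0.8 to 1.0 run, which is high for all three methods because they share the same simulated data. A longer repeat of that run with model-based and sandwich errors settled near the formula value and near 5% respectively.

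**The case against.** The strongest reply is that the planned analysis is already the recommended one and that the fallback will almost certainly not be used. That stands. With 10 covariance parameters and about 476 evaluable participants, non-convergence would be surprising. As an illustration, if the fallback had a 2% chance of use (an assumed figure) and ran at 11.1%, unconditional pairwise size would be 0.98 × 5.0 + 0.02 × 11.1 = 5.1%.

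The second reply is that nothing in the documents says the SD rises. That also stands. A reader might infer that the fallback itself runs at 7 to 11%. It does so only with a rising SD, and an honest range covers both sides of 5%.

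A reader might also blame the independent structure for the inflation. The near-identical sizes across all four structures rule that out. Its missing-data fault is real but small: at about 5% drop-out, some 125 − 119 = 6 participants per arm lack the endpoint, and independence is reached only after the other three fallbacks have failed.

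Nor does the interim analysis raise the stakes. SAP 4.10.1.6 spends no alpha there and says the interim results will not affect study conduct.

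One further reply is fair: simply deleting the independent structure would leave no rule if every heterogeneous structure failed. The fix therefore needs a terminal step.

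**Conclusion.** The point holds as a narrow, conditional gap of low severity. If the unstructured model fails to converge, every listed alternative combines a common variance with model-based errors, and Visit 10 inference is miscalibrated whenever variance differs by visit. For rising SDs the pairwise type I error is about 7 to 11% (7.7% for a Visit 7 SD of 0.8 and 11.1% for 0.6, against 1.0 at Visit 10), and the gating overall test is inflated more. For equal SDs it is 5%, and for falling SDs about 2 to 3%. These sizes rest on assumed SD patterns, near-complete data and the usual definitions of the named structures.

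The documents do not support the stronger conclusion that the primary test, as planned, exceeds 5%. The unstructured analysis is unaffected.

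**What to change.** Replace the fallback sentence in SAP 4.10.1.1 with:

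> Try in order heterogeneous Toeplitz, heterogeneous AR(1) and heterogeneous compound symmetry; if none converges, use compound symmetry. For any structure other than unstructured, use the empirical (sandwich) variance, with between-within degrees of freedom in place of Kenward-Roger.

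Drop the independent structure. Compound symmetry as the last step has two covariance parameters and still borrows from earlier visits, and the sandwich variance protects the standard error there.

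The cost is one sentence in a new SAP version, which SAP section 1 allows before database lock. Kenward-Roger is lost in the fallback branch, which is immaterial at about 119 participants per arm. Heterogeneous Toeplitz has 4 + 3 = 7 parameters against 4 for ordinary Toeplitz, so it is nearer to the model that has just failed and may fail too; the later steps cover that. The planned primary analysis does not change.

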# 4.10.1.2 Sensitivity Analysis of primary efficacy endpoint

The analysis described in Section 4.10.1.1 will be repeated for the PPS.

# 4.10.1.3 Analysis of the secondary efficacy endpoint - Dose-Response Analysis

The dose-response analysis will be conducted according to the "Dose/exposure-response analysis plan for AZD9977 and dapagliflozin in patients with heart failure and chronic kidney disease (CKD)."

#### 4.10.1.4 Multi-centre Studies

No per centre (where the term 'centre' defines each investigator site) summaries or analyses will be made.

### 4.10.1.5 Multiple Comparisons/Multiplicity

The type I error will be controlled at a 2-sided  $\alpha$ =0.05 level for multiplicity. Statistical significance will be assessed in the pre-specified order of the endpoints as specified below. The testing procedure will continue down the hierarchy if the preceding null hypothesis is rejected at a 2-sided  $\alpha$ =0.05 level and will stop if the null hypothesis for the preceding endpoint is not rejected at a two-sided  $\alpha$ =0.05 level.

- 1. Overall comparison of the percentage changes from baseline in UACR at week 12 across all 4 treatment groups (global null hypothesis)
- 2. Each of the 3 doses of AZD9977 in combination with dapagliflozin 10 mg versus dapagliflozin 10 mg in the following order:
  - a. AZD9977 150 mg + dapagliflozin 10 mg versus dapagliflozin 10 mg
  - b. AZD9977 50 mg + dapagliflozin 10 mg versus dapagliflozin 10 mg
  - c. AZD9977 15 mg + dapagliflozin 10 mg versus dapagliflozin 10 mg

TP-GDO-WW-016-08 CONFIDENTIAL Project Document Version No. 3.0 Effective Date: 26 Nov 19 Project Document Effective Date: Date of last signature Related to: SOP-GDO-WW-019 Page 24 of 50

### 4.10.1.6 Interim Analyses

An interim analysis will be performed when 300 patients have been treated for 12 weeks, unless the planned date of the interim analysis is too close to the expected data base lock date, for the complete study. The purpose of the interim analysis is to have the possibility to trigger Phase 3 activities; therefore, there will be no alpha spent. The conduct of the study will not be impacted by the results of the interim analysis. Descriptive summaries and the analysis methods for the outputs required for the interim analysis will follow the methodology outlined in this SAP. The outputs deliverables and the procedures for the provision and communication of the planned interim analysis will be provided in an Interim Unblinded Data Review Committee Charter.

# 4.10.1.7 Examination of Subgroups

Descriptive statistics of the primary efficacy variable by treatment group and subgroup (by T2DM [Yes versus No] and by eGFR [ $<30 \text{ mL/min}/1.73 \text{ m}^2$ ; or  $\geq 30 \text{ to } <45 \text{ mL/min}/1.73 \text{ m}^2$ ; or  $\geq 45 \text{ mL/min}/1.73 \text{ m}^2$ ]) will also be produced. A forest plot by T2DM status and eGFR categories will be also presented.

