9.4.1 General Considerations

All results will be presented by treatment group and overall, with descriptive statistics appropriate to the nature of the variables.

Demographic and baseline characteristics as well as prior and concomitant medication will be presented. For continuous variables, the number of non-missing observations, mean, SD, median, first and third quartiles, minimum, and maximum will be presented. For categorical variables: counts (n) and percentages (%) (where specified) will be presented. These

summaries will be provided by timepoint of assessment as appropriate.

When change from baseline will be described, the baseline value will be, in general, the last non-missing value prior to administration of the first dose of each treatment period. Further details will be described in the SAP.

The SAS[®] version 9.4 or later will be used for the data analysis.

In general, there will be no imputation of missing data for the safety analyses. Additional details will be provided in the SAP.

Deviations from the protocol will be assessed as "important" or "not-important". Important deviations from the protocol may lead to the exclusion of participants from any of the study analysis sets. Deviations will be defined before database hard lock. Important deviations will include the following:

- Violation of inclusion and/or exclusion criteria
- Administration of prohibited concomitant medications that are expected to influence the measurement of the primary endpoint.

All protocol deviations will be discussed at the data review meeting prior to database hard lock in order to define the analysis sets for the study. All the important protocol deviations will be listed by participants. Further details will be described in the SAP.

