#### 4.2 General Presentation Considerations

Continuous data, if not otherwise specified, will be summarized in terms of number of non-missing observations, mean, standard deviation (SD), median, minimum, and maximum.

For log-normal variables, descriptive statistics will include n, mean, SD, median, minimum, maximum, geometric mean (GeoMean) and geometric coefficient of variation (GeoCV).

The minimum and maximum values will be reported to the same number of decimal places as the individual values. The mean, median, SD, Q1 and Q3 will be reported to one more decimal place than the raw data recorded in the database and the same level of precision will be used for standard error (SE), and confidence intervals (CI). In general, the maximum number of decimal places reported shall be three for any summary statistic.

Derived variables will be reported to one decimal.

Rounding should be the last operation in the treatment of data. There should be no rounding of intermediate results during the calculation of any derived value. Zeros at the end of a number should be retained.

Categorical variables will be summarized using frequencies and percentages. Unless otherwise noted, the denominator for the calculation of percentages will be the total number of participants within the respective analysis set and treatment group, as applicable.

TP-GDO-WW-016-08 CONFIDENTIAL Project Document Version No. 3.0 Effective Date: 26 Nov 19 Project Document Effective Date: Date of last signature Related to: SOP-GDO-WW-019 Page 14 of 50

Percentages will be presented to one decimal place. Percentages will not be presented for zero counts. Percentages will be calculated using the number of participants within a treatment as denominator. If sample sizes are small, the data displays will show the percentages, but any textual report will describe frequencies only.

Changes from baseline in categorical data will be summarised using shift tables where appropriate.

P-values greater than or equal to 0.001, in general, will be presented to three decimal places. P-values less than 0.001 will be presented as "<0.001".

'Baseline' is defined as the last available pre-treatment assessment when not otherwise specified.

Baseline for UACR will be the value from Pre-randomization. The value is defined as the geometric mean of 3 UACR values derived from first morning void urine samples collected on 3 consecutive days (ideally day of visit and preceding 2 days).

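### As specified, the subgroup table would report an arithmetic mean and SD of percent change in UACR, which is not the scale of the primary analysis, and the subgroup forest plot has no stated estimate

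*SAP*

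**What the plan says.** SAP 4.10.1.7 names two subgroup outputs. The first is "Descriptive statistics of the primary efficacy variable by treatment group and subgroup", the subgroups being diabetes status and three eGFR categories. The second is a plot: "A forest plot by T2DM status and eGFR categories will be also presented". The section does not give the plot's estimate, comparator, model or interval.

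The outcome is set in SAP 4.10.1: "The primary efficacy endpoint for this study is the percent change from baseline in UACR at the end of 12 weeks of study treatment". SAP 4.2 defines percent change as visit value minus baseline value, divided by baseline and multiplied by 100. SAP 4.10.1 writes the same quantity with geometric means, but these are taken over one participant's samples: "At each visit, the geometric mean of the triplicate UACR values will be computed and used for the analysis of UACR".

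SAP 4.2 also fixes the statistics: "Continuous data, if not otherwise specified, will be summarized in terms of number of non-missing observations, mean, standard deviation (SD), median, minimum, and maximum". It adds the geometric mean (GeoMean) and geometric coefficient of variation (GeoCV) when a variable is log-normal. SAP 4.10.1 calls UACR log-normal; it does not say this of percent change.

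The primary model in SAP 4.10.1.1 works on log change, back-transforms, and gives 95% CIs. It has no treatment-by-subgroup term, and SAP 4.10.1.7 does not refer to it.

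**The concern.** UACR changes are skewed, which is why the primary analysis uses logs. An arithmetic mean of individual percent changes is pulled up by a few large rises, because a fall cannot exceed 100% and a rise has no ceiling. The subgroup mean and the primary estimate would then be on different scales, and a reader who sets them side by side could take a difference of scale for a difference in effect.

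This matters most for the eGFR <30 category. SAP 1 says MRAs are contraindicated in that range, and SAP 3.1 asks for at least 20% of patients there, although under Protocol 5.1 they enter only if the safety committee so decides. SAP 4.10.1.6 adds that interim summaries follow the same methods. Whether subgroup tables are among them is left to the committee charter.

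**Working it through.** **Inputs**
- Log SD s = 1.0 and a 30% difference, from Protocol 9.2. I take s as the SD of the log change, which is an assumption. I also show s = 0.8 and 0.6, both assumed.
- Within-arm ratio to baseline r = 0.70. The protocol's 30% is a between-arm difference, so this assumes no change on dapagliflozin (r = 1.00).
- Subgroup size 25 per arm = 20% of 125 (SAP 3.1, Protocol 9.2), which assumes that the 20% is met and evenly spread.

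**The plan's own figure.** SAP 4.10.1.7 states none. To check the reading of the inputs: power = Phi(-ln 0.70 / sqrt(2/119) - 1.96) = Phi(0.3567/0.1296 - 1.96) = 78.6%, close to the stated 80%. So 30% is a ratio of 0.70 with log SD 1.0.

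**Formulas**, with log ratio ~ N(ln r, s²):
- geometric change = median = r - 1
- arithmetic mean = r·exp(s²/2) - 1
- SD = r·sqrt(exp(s²)·(exp(s²) - 1))
- share of negative values = Phi(-ln r / s)

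For r = 0.70 and s = 1.0: mean = 0.70 × 1.6487 - 1 = +15.4%; SD = 0.70 × sqrt(2.7183 × 1.7183) = 1.51, or 151 points; share negative = Phi(0.357) = 64%.

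| r = 0.70, log SD | Mean | SD (points) | Median and geometric change | Negative |
|---|---|---|---|---|
| 1.0 | +15.4% | 151 | -30% | 64% |
| 0.8 | -3.6% | 91 | -30% | 67% |
| 0.6 | -16.2% | 55 | -30% | 72% |

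**Can GeoMean be computed on percent change?** It would need every value to be positive. With 25 participants at s = 1.0 that probability is (1 - 0.639)^25, about 1e-11. So GeoMean and GeoCV are not available for this variable. They are available for UACR or for its ratio to baseline.

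**The comparator on the same scale.** Dapagliflozin with r = 1.00, s = 1.0: exp(0.5) - 1 = +64.9%. The table would show +15% beside +65%. If dapagliflozin itself changes by -10% or -20%, the AZD9977 arm has r = 0.63 or 0.56 and a mean of +3.9% or -7.7%, against 0.90 × 1.6487 - 1 = +48% or 0.80 × 1.6487 - 1 = +32%.

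**Sampling variation at n = 25, r = 0.70 (simulated).** The arithmetic mean is above zero in 66%, 38% and 8% of subgroups at s = 1.0, 0.8 and 0.6. For the geometric mean the figures are 4%, 1% and 0.1%.

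**The case against.** **The variable may be UACR itself.** The heading of Protocol 8.1.1 calls UACR the primary and secondary variable. On that reading GeoMean and GeoCV can be computed, and dividing the Visit 10 figure by the baseline figure gives a geometric change. This makes SAP 4.10.1.7 ambiguous but does not settle it: SAP 4.10.1 makes percent change the endpoint, SAP 4.10.2.1 expressly summarises percentage changes, and nothing carries the log scale or a CI for the change to the subgroups. The formula in SAP 4.10.1 could also be read at group level, but a single group ratio has no SD, median or range to tabulate.

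**The table still informs.** The median is on both SAP 4.2 lists and would be correct. The arms appear together, so the direction of benefit is kept. Both points stand. A reader might infer from +15% that a beneficial arm would look harmful. The comparator's +65% under the same assumptions, and the lower means at smaller SDs, do not support that.

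**Other outputs exist.** A reader might infer that descriptive statistics are the only subgroup efficacy output, or that no geometric estimate or CI is planned for any subgroup. Neither follows. SAP 4.10.1.7 also plans the forest plot, SAP 4.10.1.8 plans Japan outputs, and SAP 4.2 sends remaining presentation details to table shells that are not among the documents. The plot's content is unstated, which does not show that it lacks a geometric estimate.

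**Quartiles.** Both SAP 4.2 lists leave them out, which might be read as a decision to exclude them. But the same section says "The mean, median, SD, Q1 and Q3 will be reported to one more decimal place than the raw data", and Protocol 9.4.1 says "For continuous variables, the number of non-missing observations, mean, SD, median, first and third quartiles, minimum, and maximum will be presented", in a paragraph that opens with baseline data. This is a drafting inconsistency.

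**Conclusion.** The point holds as a reporting defect in the subgroup plan. Read with SAP 4.2 and 4.10.1, SAP 4.10.1.7 yields an arithmetic mean and SD of percent change, with no usable GeoMean or GeoCV, and a forest plot whose estimate is undefined. At log SD 1.0 and an assumed within-arm ratio of 0.70, the mean (+15%) differs in sign from the geometric change (-30%). At assumed log SDs of 0.8 and 0.6 the sign agrees, but the mean understates the fall, by about 26 points (-4% against -30%) and 14 points (-16% against -30%). These figures rest on log-normal changes and no change on dapagliflozin.

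The median and the between-arm comparison limit the harm. The primary test, estimate, CI and multiplicity procedure are unaffected.

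**What to change.** - **SAP 4.10.1.7, table.** Summarise each participant's Visit 10-to-baseline UACR ratio by GeoMean with 95% CI and GeoCV. Show the GeoMean and its CI as percent change with the back-transformation in SAP 4.10.1.1, beside the median. Drop the arithmetic mean and SD of percent change, or footnote them.
- **SAP 4.10.1.7, forest plot.** State that it shows the geometric mean ratio of each AZD9977 arm to dapagliflozin at Visit 10 with 95% CI, computed on the log-change scale and labelled exploratory. Fitting the SAP 4.10.1.1 model within each subgroup is preferable to raw ratios, because it keeps the baseline and cohort adjustment and the handling of missing visits.
- **SAP 4.10.2.1 and 4.10.2.2.** Use the same ratio-scale summary for the descriptive percent changes in UACR and NT-proBNP. Both already have model-based analyses.
- **SAP 4.2.** Add the quartiles to the lists, as an editorial alignment only.

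The cost is a new SAP version before database lock, which SAP 1 provides for, with shell wording and minor programming. No new data are needed. Subgroup estimates stay imprecise: at n = 25 and log SD 1.0 the relative SE of one arm's geometric mean is about 1/sqrt(25) = 20%.
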